6.2.2 Radiation Therapy

The dosing and administration of radiation therapy will be in accordance with standard clinical practice guidelines for the treatment of breast cancer.

6.2.3 Dose Modifications and Delays for Endocrine Therapy

Dose Modifications

No dose modifications of endocrine therapy are permitted.

Dose Delays

Neo-adjuvant Endocrine Therapy

No dose delays will be prescribed during pre-operative endocrine therapy.

Adjuvant Endocrine Therapy

Individuals may temporarily discontinue adjuvant endocrine therapy if recommended by the treating medical oncologist. Interruptions in adjuvant endocrine therapy should not last longer than 12 weeks per year. This is based on evidence from the SOLE trial in which patients on intermittent endocrine therapy (defined as at least 9 months per year) had no difference in survival compared to those on continuous endocrine therapy³⁹.

6.3 Preparation/Handling/Storage/Accountability

6.3.1 Acquisition and Accountability

All endocrine therapy drugs will be commercially available. Individuals will receive a prescription for the endocrine drugs and the drugs will be dispensed from a licensed pharmacy. The cost of the drugs will be billed to the participant or the participant's insurance provider.

6.3.2 Formulation, Appearance, Packaging, and Labeling

Details may be found in the prescribing information for each endocrine therapy drug.

6.3.3 Product Storage and Stability

Details may be found in the prescribing information for each endocrine therapy drug.

6.4 Study Intervention Compliance

Participants will be asked about compliance with taking endocrine therapies as part of patient reported outcomes.

6.5 Registration and Treatment Allocation

All participants must sign the consent form prior to determination of eligibility for this study.

Pre-Operative Window of Adjuvant Endocrine Therapy to Inform Radiation Therapy Decisions in Older Women with Early-Stage Breast Cancer

Version Date: 21 February 2023

When a site is ready to enroll a patient, the following documentation must be scanned and emailed to the UVA Coordinating Center:

- Patient and staff signed signature page of the current informed consent form (ICF)
- Completed Inclusion/Exclusion checklist demonstrating subject eligibility
- Supporting documentation needed to confirm eligibility (lab results, scan results etc.)

Consult with the MCRO for instructions on sending this information. The Coordinating Center will consult with the Overall Study PI if questions arise in confirming eligibility. The UVA Coordinating Center will communicate the subject number to the enrolling site.

Registration will occur following verification of eligibility by the treating physician.

Participants who are consented and accrued to the study should be registered in OnCore in accordance with the Clinical Trial Management System Policy via the UVa OnCore Resources link in OnCore. General guidelines are available in the OnCore User Manual and Data Entry Guide.

Participants should receive their first study treatment within 2 weeks of registration.

Treatment allocation to receive either radiation and adjuvant endocrine therapy or adjuvant endocrine therapy after BCS will be discussed with participants during the process of informed consent. At enrollment and at the pre-operative visit, the surgical oncologist will be asked the radiation recommendation survey question ([section 8.2.2](#)). If the patient is seen by UVA radiation oncology during this time, the radiation oncologist will be asked the radiation recommendation survey question at enrollment and at the time of the pre-operative visit ([section 8.2.2](#)). The participant will also answer a radiation preference survey question at enrollment and at the pre-operative visit ([section 8.2.2](#)). Individuals will proceed with/without radiation and adjuvant endocrine therapy per standard clinical practice.

This study does not involve any randomization, blinding or masking procedures. Participants will be told which treatment they are receiving.

6.6 Concomitant Therapy

For this protocol, a prescription medication is defined as a medication that can be prescribed only by a properly authorized/licensed clinician. The participant should be asked about all medications that were administered ≤ 28 days prior to screening and throughout study treatment.

6.6.1 Prohibited Concomitant Medications

- Endocrine therapy not prescribed for the treatment of the breast cancer
- Current use of strong CYP2D6 inhibitors if participant is receiving tamoxifen.

6.6.2 Rescue Medicine/Supportive Care

Any reported side effects from the endocrine therapy should be managed by the treating physicians per usual standard of care. This includes recommendations for non-medication

Version Date: 21 February 2023

supportive interventions such as acupuncture, physical therapy, etc. Physicians may also choose to prescribe additional medication with evidence for improving endocrine therapy side effects such as venlafaxine, duloxetine, or Nonsteroidal anti-inflammatory drugs. Any prescription medications will be prescribed per package labeling. Patients on endocrine therapy should have any routine standard of care monitoring as recommended by the treating oncologist. This includes annual LFT evaluation and annual gynecology evaluation for patients on tamoxifen if recommended by treating oncologist. This includes periodic assessment of bone density and appropriate treatment of low bone density as recommended by the treating oncologist.

7 STUDY CLOSURE, STUDY INTERVENTION DISCONTINUATION AND PARTICIPANT DISCONTINUATION OR WITHDRAWAL

7.1 Study Discontinuation and Closure

This study may be temporarily suspended or prematurely terminated if there is sufficient reasonable cause. Written notification, documenting the reason for study suspension or termination, will be provided by the suspending or terminating party to the investigator and funding agency. If the study is prematurely terminated or suspended, the Principal Investigator (PI) will promptly inform the Institutional Review Board (IRB) and will provide the reason(s) for the termination or suspension. Study participants will be contacted, as applicable, and be informed of changes to study visit schedule.

Circumstances that would warrant termination or suspension include, but are not limited to:

- Determination of unexpected, significant, or unacceptable risk to participants
- Demonstration of efficacy that would warrant stopping
- Insufficient compliance to protocol requirements
- Data that are not sufficiently complete and/or evaluable
- Determination of futility

For safety related concerns, the study may resume once concerns about safety, protocol compliance, and data quality are addressed, and satisfy the Principal Investigator, IRB, and Data and Safety Monitoring Committee.

Participants receiving study treatment at the time of study discontinuation should complete procedures described in [section 7.3](#).

7.2 Participant Discontinuation/Withdrawal

Participants are free to withdraw from participation in the study at any time upon request.

A participant's study treatment would be discontinued for the following reasons:

- If any clinical adverse event (AE), laboratory abnormality, or other medical condition or situation occurs such that continued participation in the study would not be in the best interest of the participant per the discretion of the principal investigator.
- Disease progression which requires discontinuation of the study intervention

Pre-Operative Window of Adjuvant Endocrine Therapy to Inform Radiation Therapy Decisions in Older Women with Early-Stage Breast Cancer

Version Date: 21 February 2023

- If the participant meets an exclusion criterion (either newly developed or not previously recognized) that precludes further study participation
- Participant decision to withdraw from study treatment and/or the study
- Initiation of prohibited intervention or medication
- Dose delays beyond those permitted in [section 6.2.3](#)

The reason for participant discontinuation or withdrawal from study treatment will be recorded on the CRF. Participants who sign the informed consent and who are registered will not be replaced. Participants that withdraw from the study (not only from study treatment, but all study follow-up) will not be contacted for any further study visits.

7.3 Procedures for Discontinuation of Study Intervention

Discontinuation from endocrine therapy or radiation therapy does not mean discontinuation from the study, and remaining study procedures should be completed as indicated by the study protocol. If a clinically significant finding is identified (including, but not limited to changes from baseline) after enrollment, the investigator or qualified designee will determine if any change in participant management is needed. Any new clinically relevant finding will be reported as an adverse event (AE).

The data to be collected and procedures to be completed at the time of study intervention discontinuation are included in the schedule of events ([Appendix 1](#)).

7.4 Lost to Follow-Up

A participant will be considered lost to follow-up if she fails to return for 3 scheduled visits and is unable to be contacted by the study site staff. The study staff will attempt to contact the participant up to 3 times.

The following actions must be taken if a participant fails to return to the clinic for a required study visit:

- The site will attempt to contact the participant and reschedule the missed visit within 4 weeks and counsel the participant on the importance of maintaining the assigned visit schedule and ascertain if the participant wishes to and/or should continue in the study.
- Before a participant is deemed lost to follow-up, the investigator or designee will make every effort to regain contact with the participant by phone.
- These contact attempts should be documented in the study file.
- Should the participant continue to be unreachable, she will be considered to have withdrawn from the study with a primary reason of lost to follow-up.

8 STUDY ASSESSMENTS AND PROCEDURES

8.1 Clinical Assessments

The study team will have access to tests and procedures conducted prior to the study that were completed as part of an individual's standard clinical care. These include information about medical history, results from prior physical exams or laboratory tests, pathology reports, and clinic notes.

Pre-Operative Window of Adjuvant Endocrine Therapy to Inform Radiation Therapy Decisions in Older Women with Early-Stage Breast Cancer

Version Date: 21 February 2023

The following evaluations will be performed on an outpatient basis. Please refer to [Appendix 1](#) for the schedule of activities.

8.1.1 Exams and Evaluations

The following will be performed by a licensed clinician:

- Medical History
- Physical Exam -Breast exam and axillary lymph node exam.
- Vital signs (pulse, blood pressure)
- Start and stop dates of pre-ET and adjuvant endocrine therapy; reason for discontinuation

8.1.2 Assessment of Adverse Events

Each participant will be evaluated by a licensed clinician at each study visit. The NCI Common Terminology Criteria for Adverse Events (CTCAE) version 5 will be used for the characterization and grading of adverse events.

Toxicities will be captured from the exams and evaluations. For each AE, date of onset, duration, grade, and attribution will be noted in the individual's study chart, or study documents, or in the clinic note and will be entered in the UVA Cancer Center database.

In the event of an AE, appropriate action will be taken to ensure adequate care for the participant. If the participant is still on protocol, treatment delay or withdrawal from the protocol will be considered according to the protocol guidelines ([section 6.2.3](#)).

8.2 Participant Questionnaires

8.2.1 Patient Belief Surveys

Baseline data regarding patient beliefs and perceptions about their breast cancer and endocrine therapy will be collected prior to starting pre-ET.

The Brief Illness Perception Questionnaire (BIPQ, [Appendix 3](#)) is a 9 item scale that measures patients' beliefs about their illness including consequences, timeline, personal control, treatment control, identity, coherence, emotional response, and causes⁴⁰. Responses are on a 10 point Likert scale and patients also identify 3 causes of their breast cancer.

The Beliefs about Medicines Questionnaire (BMQ) is an 8 item scale that measures patients' beliefs about medicines using a 5-point Likert scale⁴¹. The BMQ-ET ([Appendix 4](#)) is an adapted version of the BMQ that includes 10 questions on a 5 point Likert scale that assess patients' beliefs about their endocrine therapy⁴². The BMQ-ET will be assessed at baseline.

The Perceived Sensitivity to Medicine Scale (PSM, [Appendix 5](#)) is a 5 item assessment of patients' perceived sensitivity to medications at baseline using a 5 point Likert scale⁴³.

The UVA Breast Cancer Belief Survey ([Appendix 6](#)), a novel series of questions regarding patient beliefs about breast cancer and breast cancer medications, will also be administered.

Pre-Operative Window of Adjuvant Endocrine Therapy to Inform Radiation Therapy Decisions in Older Women with Early-Stage Breast Cancer

Version Date: 21 February 2023

8.2.2 Radiation Preference Questions

The patient and the surgical oncologist will answer the radiation preference question at enrollment and at the pre-operative visit. If the patient has a radiation oncology consultation on or before Day 1, the radiation oncologist will answer the radiation preference question at Day 1 and at the pre-operative visit per [Appendix 1](#). Answers to questions are measured on a 4 point Likert scale. Before IRB approval of protocol version 01-27-2021, radiation preference questions were asked at a post-operative visit and not the pre-operative visit. Subjects who have had their pre-operative visit but not their post-operative visit after protocol v 01-27-2021 is IRB approved should have their radiation preference questions asked post-operatively to ensure that this data point is collected.

Enrollment Patient Question: Based on the conversations you have had with your breast cancer doctors thus far, how likely are you to decide to do radiation after your surgery?

Enrollment Surgical/Radiation Oncologist Question: Based on your current knowledge of this patient's breast cancer and discussions with her about her treatment plan, how would you characterize the strength of your recommendation for adjuvant radiation therapy?

Pre-operative Patient Question: Based on the conversations you have had with your breast cancer doctors thus far and your experience with the breast cancer medicine taken before surgery, how likely are you to decide to do radiation after your surgery?

Pre-operative Surgical/Radiation Oncologist Question: Based on your current knowledge of this patient's breast cancer, discussions with her about her treatment plan, and her experience with pre-ET, how would you characterize the strength of your recommendation for adjuvant radiation therapy?

8.2.3 Patient Reported Outcome Surveys

Patient reported outcomes will be assessed as indicated in [Appendix 1](#).

Health related quality of life (HRQOL) will be assessed using the EORTC QLQ-C30 and QLQ-BR23 ([Appendix 7](#)), which is a validated and reliable 53 question assessment of general health and wellbeing⁴⁴.

Depression will be assessed using the Center for Epidemiologic Studies Depression Scale Revised (CESD-R, [Appendix 8](#)), which is a 20 item assessment to measure symptoms of depression in nine different groups as defined by the American Psychiatric Association Diagnostic and Statistical Manual, fifth edition. The score ranges from 0 to 60 and scores greater than 16 indicate depressive symptoms⁴⁵.

Pre-Operative Window of Adjuvant Endocrine Therapy to Inform Radiation Therapy Decisions in Older Women with Early-Stage Breast Cancer

Version Date: 21 February 2023

General symptom burden while on endocrine therapy will be assessed using the Breast Cancer Prevention Trial Symptom Checklist (BCPT-SCL, [Appendix 9](#)) in which 47 symptoms are assessed on a scale of 0 to 4 (high burden) with plans to follow symptom clusters used in the ELPh trial of weight/body image, vasomotor, vulvovaginal, musculoskeletal, cognitive, and mood^{33,46,47}.

Data will be collected on patient adherence to endocrine therapy using patient report via two simple questions ([Appendix 10](#)).

8.2.4 Treatment Decision Survey

A survey to assess treatment decision will be given as indicated in [Appendix 1](#). The survey can be found in [Appendix 11](#).

8.2.5 Decisional Conflict and Decision Regret Scales

The Decisional Conflict Scale (DCS)⁴⁸ and Decision Regret Scale (DRS)⁴⁹ are patient reported outcome surveys that will be used to assess subjects' perceptions related to their medical choices ([Appendix 12](#) and [Appendix 13](#)). The DRS does not need to be completed at baseline because it relates to past decisions related to a medical choice (radiation and endocrine therapy) that is not made at baseline.

8.3 Recurrence and Survival

Recurrence is defined as a biopsy-proven diagnosis of breast cancer in the index quadrant of the previously treated breast cancer. Patients will be evaluated routinely post-treatment to assess for local recurrence, loco-regional recurrence, contralateral breast cancer recurrence and distant disease. Clinical breast exams will be performed per standard of care every 3-6 months by the treating physicians. Mammography will be performed annually if patient is still eligible for breast cancer screening based on standard practice guidelines and images will be reviewed for evidence of recurrence.

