2.2 Background

2.2.1 Breast Conservation Therapy is a Standard Treatment for Early Stage Breast Cancer

Early stage breast cancer is treated with surgery (mastectomy or BCS). There is no difference in long term survival between mastectomy and breast conservation therapy (BCS followed by radiation therapy (RT); BCT), and BCT is the preferred treatment approach based on decreased morbidity and higher associated quality of life^{10,11}. Traditionally, a key part of BCS is the recommendation for adjuvant whole breast RT to decrease the risk of local recurrence¹²⁻¹⁴. Adjuvant RT is delivered in the immediate post-operative period as there is evidence of increased risk of local failure if RT is delayed beyond 8 weeks¹⁵⁻¹⁷. Patients with hormone receptor positive breast cancer are treated with adjuvant endocrine therapy (tamoxifen or an AI), which is typically started upon completion of RT. The duration of endocrine therapy is at least 5 years with evidence for extended duration in higher risk patients¹⁸. Adjuvant endocrine therapy is proven to decrease local recurrence, distant recurrence, and prolong survival¹⁹.

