reasons for why providers do not offer RT omission is multifactorial. Providers overestimate the life expectancy of patients⁶ and believe that healthy patients over age 70 do not fit the population of the CALGB 9343 study. In fact, the patients in CALGB 9343 were healthier and lived longer than women in the general population of similar ages². A key part of the design of CALGB 9343 and PRIME II trials was that all patients were recommended to be treated with adjuvant endocrine therapy. Adjuvant endocrine therapy is shown to not only decrease distant recurrence, but also IBTR¹²⁻¹⁴. When recommending BCS with omission of immediate postoperative RT, neither the provider nor the patient knows whether the patient will tolerate and adhere to prescribed endocrine therapy. Early insight regarding an individual patient's tolerance and predicted adherence to endocrine therapy has potential to assist physicians to better formulate treatment plans and will allow patients to better accept and follow these recommendations. This would result in a patient specific treatment plan and decrease the risk of either over or under treatment of early stage breast cancer in the geriatric population.

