3 OBJECTIVES AND ENDPOINTS

Objectives	Endpoints
Primary	

• To assess whether pre-ET changes an individual's preference for adjuvant radiation treatment• To assess whether pre-treatment with endocrine therapy changes the surgical oncologist's preference for adjuvant radiation treatment	
• Radiation preference question for participant pre and post pre-ET treatment• Radiation preference question for the surgical oncologist pre and post pre-ET treatment
Secondary	

• To obtain preliminary estimates to assess whether patient reported outcomes during pre-ET are predictive of long-term adjuvant endocrine therapy adherence• For those participants who agree to a radiation oncologist consultation, to assess whether pre-treatment with endocrine therapy changes the radiation oncologist's preference for adjuvant radiation treatment	
• PRO assessments• Radiation preference question for the radiation oncologist pre and post pre-ET treatment
Exploratory	

• To obtain preliminary data on the effect of pre-ET on decision outcomes for adjuvant therapy after BCS	
• PRO assessments
Exploratory	

• To obtain exploratory data on recurrence-free survival and overall survival	
• Recurrence-free survival and survival through 24 months

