Descriptive summaries and simple tabulations will be used to describe results from the preliminary data on justification of participant response for those whose preference changed.

At final analysis the Product-Limit method of Kaplan & Meier will be used to estimate recurrence-free survival and overall survival, along with 90% CIs. Recurrence-free survival is defined as the time from start of pre-ET to time of recurrence or death from any cause, whichever occurred first. Participants who do not experience an event (recurrence or death) will be censored at date of last clinical assessment. Overall survival is defined as the time from start of pre-ET to time of death from any cause. Participants who do not experience an event (death) will be censored at date of last contact.

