Appendix 1: Schedule of Events

Procedures	Screening	Pre_ET Period ^c			Pre-Op Visit	Surgery ⁱ	Radiation	Adjuvant Treatment Period			
Timeframe	≤ 21 days prior to registration unless otherwise noted	Day 1	Day 30 (+/- 7 d)	Day 90 (+/- 7 d)		2-8 weeks after Day 90 ^j		Visit 1 (1-90 days after surgery, chemotherapy completion, or RT completion ^b whichever is later)	Visit 2 (6 months after visit 1) (+/- 30 d)	Visit 3 (12 months after visit 1) (+/- 30 d)	Visit 4 (24 months after visit 1) (+/- 30 d)
Informed consent	X										
Demographics	X										
Medical history	X										
Physical exam /vitals	X		X	X	X			X	X	X	X
Endocrine Therapy		Taken daily as directed ⁱ						--Taken daily as directed ^d --			
BCS						X					
Radiation Therapy							X ^b				
Adverse event review and evaluation			X	X	X ^g						
Patient Beliefs Qs		X									
PRO Surveys	X ^a	X	X					X	X	X	X
Treatment Decision Survey								X			
Subject RT preference question		X			X						
Surgeon RT preference question		X ^h			X						
Radiation Oncologist RT preference question		X ^{f,h}			X ^f						
Decisional Conflict Scale		X			X						
Decision Regret Scale									X	X	X
Recurrence/Survival ^e								X	X	X	X

^a Patient reported outcome surveys should be completed prior to first dose of endocrine therapy.

^b Radiation therapy will be scheduled and administered in accordance with standard clinical practice and as recommended by the treating radiation-oncologist.

^c For patients who do not tolerate pre_ET and discontinue early, they will continue to be followed as indicated in the schedule above beginning at the pre-op visit.

Pre-Operative Window of Adjuvant Endocrine Therapy to Inform Radiation Therapy Decisions in Older Women with Early-Stage Breast Cancer

Version Date: 21 February 2023

^d Some individuals may choose to refuse adjuvant endocrine therapy, but will continue to be followed as indicated in the schedule above. Some Individuals will continue beyond 24 months of endocrine therapy as directed by their oncologist based on standard of care recommendations.

^e Tumor imaging will not be required at visits 1-4 to assess recurrence. Recurrence will be assessed using data from breast examinations conducted during the visit and prior results from imaging completed as part of standard clinical practice.

^f This is not applicable if participant has not been seen by Radiation Oncology prior to starting pre-ET (radiation oncology consultation on or before Day 1).

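### Recurrence is defined as biopsy-proven index-quadrant disease only, so exploratory recurrence-free survival misses other-quadrant, regional and distant recurrences in living women

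*Combined protocol and SAP*

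**What the plan says.** Section 8.3 defines the term: "Recurrence is defined as a biopsy-proven diagnosis of breast cancer in the index quadrant of the previously treated breast cancer". Two conditions must be met, biopsy proof and location in the index quadrant. The next sentence of 8.3 lists what routine follow-up looks for: "local recurrence, loco-regional recurrence, contralateral breast cancer recurrence and distant disease". It does not say whether those findings are endpoint events.

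Section 10.5.2 defines the endpoint: "Recurrence-free survival is defined as the time from start of pre-ET to time of recurrence or death from any cause, whichever occurred first". It gives the censoring rule: "Participants who do not experience an event (recurrence or death) will be censored at date of last clinical assessment". It neither redefines recurrence nor lists sites.

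Section 3 places the endpoint among the exploratory ones: "Recurrence-free survival and survival through 24 months". Section 10.5.2 reports it by Kaplan-Meier with 90% confidence intervals and no test. Footnote e of Appendix 1 describes how recurrence is found ("Recurrence will be assessed using data from breast examinations conducted during the visit and prior results from imaging"). It adds no sites and does not mention confirmation.

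**The concern.** RFS that counts only index-quadrant disease and death does not carry the meaning its name suggests. A woman alive with biopsy-proven distant metastases would be analysed as recurrence-free.

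The narrow definition also disagrees with how the protocol uses the word elsewhere. Section 8.3 itself applies it to loco-regional and contralateral disease. Section 2.2.1 states: "Adjuvant endocrine therapy is proven to decrease local recurrence, distant recurrence, and prolong survival". Section 2.2.3 states: "Adjuvant endocrine therapy is shown to not only decrease distant recurrence, but also IBTR". The abbreviation list expands IBTR as recurrence in the ipsilateral breast, with no quadrant limit.

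At stake is a reported 24-month RFS that is too favourable for what readers will take it to mean. An analyst would also have to choose between an explicit definition and an inferred wider one, possibly after seeing the data.

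**Working it through.** **Applying the text.** The plan states no RFS figure, so there is none to reproduce. Taking the 8.3 definition into the 10.5.2 event and censoring rules gives:

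| Finding in a living woman | Recurrence under 8.3? | RFS status under 10.5.2 |
|---|---|---|
| Index quadrant, biopsy-proven | Yes | Event |
| Index quadrant, no biopsy | No | Censored |
| Other quadrant, same breast | No | Censored |
| Regional nodes | No | Censored |
| Contralateral breast | No | Censored |
| Distant | No | Censored |

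If she later dies, the death counts, dated at death. The 24-month estimate is therefore affected only for women still alive without a counted event at that point. No other section adds sites to the event.

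**Inputs for the size.** N = 83 is the maximum target (10.4) and N = 70 the evaluable number (10.3). Let c be the number of events that are counted. Assume all other women are followed to 24 months.

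**One omitted event.**

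- RFS with the event counted: (N − c − 1)/N.
- As written, censored after all counted events: (N − c)/N. Shift = 1/N.
- As written, censored before all counted events: (N − 1 − c)/(N − 1). Shift = (N − 1 − c)/[N(N − 1)].

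| N | c | Counted | As written, late censoring | As written, early censoring | Shift (points) |
|---|---|---|---|---|---|
| 83 | 3 | 79/83 = 95.18% | 80/83 = 96.39% | 79/82 = 96.34% | 1.20 or 1.16 |
| 83 | 4 | 78/83 = 93.98% | 79/83 = 95.18% | 78/82 = 95.12% | 1.20 or 1.15 |
| 70 | 3 | 66/70 = 94.29% | 67/70 = 95.71% | 66/69 = 95.65% | 1.43 or 1.37 |
| 70 | 4 | 65/70 = 92.86% | 66/70 = 94.29% | 65/69 = 94.20% | 1.43 or 1.35 |

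Over c = 0 to 4 the shift is 1.15 to 1.20 points at N = 83 and 1.35 to 1.43 at N = 70. The timing of censoring hardly matters.

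**Several omitted events (assumed number, late censoring).** One, two or three omitted events give 1.20, 2.41 or 3.61 points at N = 83, and 1.43, 2.86 or 4.29 points at N = 70.

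**How many are plausible.** Section 2.2.3 gives rates only for wider categories:

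- local and regional recurrence, 2% and 10% at a median 12.6 years;
- IBTR, 1.3% and 4.1% with a median follow-up of 5 years;
- local recurrence, 0.9% and 9.8% at 10 years.

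Assume a constant hazard and similar risk in this trial. Expected events over 2 years in 83 women are then 83 × [1 − (1 − p)^(2/T)]. The lowest is p = 0.009, T = 10, which gives 0.15. The highest is p = 0.098, T = 10, which gives 1.69. These totals include index-quadrant events that 8.3 already counts, and exclude distant disease, for which no rate is given.

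**The case against.** The strongest reply is that the wider intent is plain. The sentence after the definition puts local, loco-regional, contralateral and distant disease under surveillance, so a broader RFS could be derived if those findings are recorded. On this view, 8.3 is one loosely drafted paragraph. That stands as a reading of intent. It does not remove the defect, because a list of what is looked for is not a list of events, and the explicit definition still governs the analysis.

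A second reply is that the estimate is unbiased for its own definition, and that a local focus suits a trial about omitting radiation. The first half is correct: the overstatement is relative to all-site RFS. The second half would justify a whole-breast endpoint but does not explain the index quadrant, and a local-control endpoint should not be called recurrence-free survival.

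Third, the background statements on endocrine therapy carry little weight for consequence. The study has no control arm, and section 2.4.1 disclaims any aim to show better efficacy than upfront surgery. That is fair. Those statements show how the protocol uses the word; they do not show that an efficacy conclusion is at risk.

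Fourth, three omitted events looks unlikely. For in-breast and regional disease the rates above support that, with probably about one omitted event or none. Three would mostly require distant disease. The per-event shift is the safer figure to carry forward.

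**Conclusion.** The concern holds. The definition in 8.3, carried into 10.5.2, produces an RFS that omits other-quadrant, regional and distant recurrence in living women, and no other section repairs it. The error runs one way, towards a higher RFS than an all-site definition would give. The size is about 1.2 points per omitted event at N = 83 and 1.4 at N = 70, assuming the other women are followed to 24 months. The number of such events cannot be derived from the documents.

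Severity is minor. The endpoint is exploratory and untested, and nothing in the primary or secondary analyses, the sample size or the pausing rules rests on it.

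**What to change.** In 8.3 and 10.5.2, define the RFS event as the first ipsilateral breast recurrence in any quadrant, regional recurrence, distant recurrence, or death from any cause. State whether contralateral cancer counts. State what proof is accepted for each type, using information from standard care. Report index-quadrant recurrence as a separately named component. If only local control is intended, rename the endpoint so that it is not reported as RFS. Adding the confirmation step to footnote e of Appendix 1 is optional, since the footnote does not contradict 8.3.

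The cost is wording and a short proof rule per event type, settled before the final analysis. Section 8.3 already provides for assessment of these sites, and Appendix 1 already schedules recurrence and survival at adjuvant Visits 1 to 4, so no visits or imaging are added. There are two downsides. RFS may look slightly less favourable, and distant events found only through standard care may still be under-ascertained, which the report should say.
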